6.4 Engraftment Samples

Follicular engraftment sampling will be completed via use of Biore® Strips applied across the bridge of the nose extending to either cheek at Visits 1/Screening and Visit 5/EOT. Results will be reported as both a genotype assessment and as absence or presence of live NB01. Skin surface engraftment sampling will be completed via cheek swab at each visit. Three genotypes (deoR, Cas5, Transposase2) will be assessed and reported as the percentage of total bacteria count (PanBac) for both the follicular and skin surface engraftment samples.

6.5 Sebum Production

Sebum production ($\mu\text{g}/\text{cm}^2$) is measured at the mid-glabellar region of the forehead using a Sebumeter at each visit at sites 02 and 03.

7. SAFETY EVALUATIONS

7.1 Adverse Events

All reported or observed adverse events (AEs) will be recorded. At each visit, subjects will also be questioned specifically about the status of any ongoing AEs. Untoward events that occur prior to the first dose of study drug will be captured in the medical history unless they are related to a study-specific procedure. AEs will be assessed from the time of consent.

7.2 Local Skin Reactions

Local skin reactions (LSRs) will be assessed at each visit using a four-point ordinal scale: 0-absent, 1-mild (slight, barely perceptible), 2-moderate (distinct presence) and 3-severe (marked, intense). The investigator will assess erythema, edema, erosion/ulceration, scaling/dryness, and scabbing/crusting in the treatment area. Subjects will assess itching and pain in the treatment area. LSRs that require medical intervention, withholding or discontinuation of study drug application, or extend 2 cm beyond the treatment area will be documented as AEs.

In addition to the clinic visit assessments, subjects will maintain a daily diary to assess each of the seven LSR parameters. The subjects are to record the greatest severity of each LSR experienced during the previous 7 days (weekly score for Weeks 1 through 16).

7.3 Physical Examination

The limited physical examination will include examination of the face, chest, arms, and back (i.e., relevant acne regions). Abnormalities at Screening/Baseline will be recorded as medical history. Any new or worsening abnormalities at Visit 5/EOT will be recorded as AEs.

7.4 Vital Signs

Vital signs including blood pressure, heart rate, and temperature will be measured at Screening/Baseline and Visit 5/EOT.

7.5 Pregnancy Test

A urine pregnancy test (UPT) will be performed at Screening/Baseline and Visit 5/EOT for women of childbearing potential (WOCBP).

7.6 Complete Blood Count

The complete blood count (CBC) will be assessed locally at Screening and Visit 5/EOT and must include Differential.

8. STATISTICAL METHODS

8.1 General Considerations

All statistical processing will be performed using SAS[®] version 9.4. Summary tables (descriptive statistics and/or frequency tables) will be provided for screening and/or baseline variables, efficacy variables, and safety variables. Summaries will be provided for each treatment group. In general, continuous variables will be summarized by descriptive statistics including sample size, mean, SD, median, minimum, and maximum. Categorical variables will be summarized by frequency and percentage.

In general, all tables will be supported by relevant listing (by-subject). Figures may be created to aid in the interpretation of results.

The by visit data analyses will be summarized and analyzed using the visit window for modified intent-to-treat (mITT) and per-protocol (PP) populations based on target day as shown in Table 3.

Table 3: Analyses Windows for mITT and PP Populations

Visit	Target Day	mITT Window	PP Window
Visit 1 / Screening	-28 to -1	-28 to -1	-28 to -1
Visit 2 / Baseline	1	1	1
Visit 3 / Week 2	8	2 – 21	6 – 10
Visit 4 / Week 7	43	22 – 61	36 – 50
Visit 5 / Week 12 / EOT	80	> 61	71– 90

If there is more than one measurement within a visit after windowing is applied, the one closest to the target day will be used in the analysis by visit. If a study visit is outside of the window in PP analyses, it will be treated as missing data.

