6.2. Pretreatment Assessments

6.2.1. Screening Visit – Visit 1

Subjects will be screened (Day -14 to Day -1) before randomization to determine eligibility for participation in the study. The following will be performed and documented at the Screening Visit:

- Obtain a signed, written informed consent.
- Review inclusion/exclusion criteria and confirm subject eligibility.
- Record medical history.
- Record prior and/or concomitant medications, topical facial products and procedures/therapies.
- Have subject complete washout from any prohibited medications, if necessary.
- Limited physical examination.
- Vital signs.
- UPT.
- Local CBC.
- Pre-Treatment with BPO of at least 5, but no more than 7, consecutive days (Screening)
- Dispense Subject Diary (for completion of at-home Cetaphil® BID washes and BPO QD application).

- Sebum levels, measured at the mid-glabellar region of the forehead using a Sebumeter SM – 815 (COURAGE + KHAZAKA electronic GmbH, Köln, Germany).
- Assess AEs.
- Assess LSRs.
- IGA.
- Acne Lesion Counts (total, inflammatory, and non-inflammatory lesion counts).
- Quality of life assessment (Acne QoL Questionnaire).
- Optional facial photography.
- Cheek swab skin engraftment sample.
- Face wash with Cetaphil®.
- Biore® strip follicular engraftment sample.
- Schedule the Visit 2/Baseline visit.

Subjects meeting all of the inclusion criteria and none of the exclusion criteria will return to the clinic after screening for randomization into the study on Day 1.

From the time of obtaining informed consent through the first administration of study drug, record all serious adverse events (SAEs), as well as any AEs related to protocol-mandated procedures on the AE eCRF. All other untoward medical occurrences observed during the screening period, including exacerbation or changes in medical history are to be captured on the medical history CRF/eCRF. See [Section 7](#) (Adverse Event Reporting and Toxicity Management) for additional details.

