6.2.5. Unscheduled Visit

The following will be performed and documented at unscheduled visits:

- Review Subject Diary. NOTE: In review of the Subject Diary, the PI should question the subject to gauge understanding of application instructions, and re-instruct, as needed.
- Sebum levels, measured at the mid-glabellar region of the forehead using a Sebumeter SM – 815 (COURAGE + KHAZAKA electronic GmbH, Köln, Germany).
- Assess AEs.
- Assess LSRs.
- Review concomitant medications, topical facial products and procedures/therapies.
- Limited physical examination.
- Vital signs.
- UPT.
- Local CBC.
- IGA.
- Acne Lesion Counts (total, inflammatory, and non-inflammatory lesion counts).
- Quality of life assessment (Acne QoL Questionnaire).
- Optional facial photography.
- Cheek swab skin engraftment sample.
- Biore® strip follicular engraftment sample.
- Confirm next scheduled visit.

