- f** Blood pressure, heart rate, temperature.
- g** CBC is assessed locally and must include Differential.
- h** Urine dipstick test assessed locally.

- i** All screening visit procedures will be completed prior to initiating BPO pre-treatment. BPO gel should be applied for at least 5 days, in the AM immediately after the AM Cetaphil® wash. Final BPO pre-treatment should be approximately 24 hours prior to application of study drug.
- j** Study subjects will note date and time of each BPO pre-treatment and Cetaphil® wash for the Screening period, and date and time for each Cetaphil® wash and study drug application during the study treatment period.
- k** Subjects must not wash, shave, apply make-up or other products to their face, and subjects must hold their application of study drug, on clinic visit days.
- l** Subjects will wash their face with Cetaphil® cleanser twice daily beginning at the Screening visit throughout the Week 12/EOT visit. No other face wash products may be used during the Subject's participation in the study.
- m** Subjects will wash with Cetaphil® at the clinic after all other Day 1 procedures have been completed and immediately prior to study drug application by the PI.
- n** Screening samples are obtained prior to initiation of BPO pre-treatment.
- o** Follicular engraftment sampling is completed via use of Biore® Strips applied across the bridge of the nose extending to either cheek.
- p** The Week 12/EOT visit will take place between 3 to 7 days following the Subject's final study drug application. The PI should inquire regarding the subjects understanding of and compliance with study drug application procedures and re-instruct, as necessary.
- q** Week 12/EOT follicular engraftment sampling will be obtained after facial washing via Biore® strip at the clinic and should be completed 3 to 7 days following the last study drug application.
- r** Study drug is applied by the PI (or sub-I designee) on Day 1; study drug is applied by the Subject daily thereafter in the evenings.
- s** Study procedures are completed as is clinically indicated for vital signs, physical exam, urine pregnancy, and CBC for unscheduled study visits.
- t** EOT procedures should be completed at the Week 12 visit. Should the subject discontinue the study prior to Week 12 (Visit 5), the EOT procedures should be scheduled and completed as soon as possible.
- u** Dispense Subject Diary to the subject.

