5. DEFINITIONS

- **Study Day:** The study day is the day of study relative to the first dose date and is calculated by follow-up visit date – first dose date + 1. For a subject who was randomized but not treated, the randomization date will be used.

- “Treatment success” for follicular engraftment assay: A post-Screening Follicular Biore sample having evidence of live NB01.

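### SAP Table 3 keeps the value nearest the target day without giving the scheduled visit precedence, so an unscheduled value taken 0-2 days after the last dose can stand in for the off-drug Visit 5

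*SAP*

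**What the plan says.** **Selection rule.** SAP 8.1 maps measurements to visits through Table 3, for the mITT and PP by-visit analyses, and continues: "If there is more than one measurement within a visit after windowing is applied, the one closest to the target day will be used". It does not rank scheduled above unscheduled records, sets no condition on days since the last dose, and has no tie-break.

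**Visit 5.** Table 3 gives target Day 80, an open-ended mITT window and a PP window of Days 71-90: "Visit 5 / Week 12 / EOT 80 > 61 71– 90". Protocol Appendix 2, footnote p, sets the off-drug gap: "The Week 12/EOT visit will take place between 3 to 7 days following the" subject's final application. Footnote q repeats the gap for the follicular strip.

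**Unscheduled visits.** Protocol 6.2.5 opens with "The following will be performed and documented at unscheduled visits". Its list includes sebum, IGA, lesion counts, QoL, cheek swab and Biore strip. Appendix 2 marks the same items, and its footnote s makes only vital signs, physical examination, pregnancy test and CBC depend on clinical need.

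**Follicular success.** SAP 5 defines it as "A post-Screening Follicular Biore sample having evidence of live NB01". SAP 3.2 and 8.9.2 place the endpoint at EOT. SAP 8.9.2 also averages the marker ratios over a visit's samples and scores success if any sample at that visit is positive.

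**Screening.** Table 3 has "Visit 1 / Screening -28 to -1 -28 to -1 -28 to -1", so the target is the whole window. Protocol 6.2.1 says: "Subjects will be screened (Day -14 to Day -1) before randomization to determine eligibility for participation in the study". Appendix 2, footnote n, adds: "Screening samples are obtained prior to initiation of BPO pre-treatment". Footnote i says the same of all Screening procedures.

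**The concern.** Visit 5 is where every MMRM comparison and the follicular comparison are made, and the design separates it from dosing by 3 to 7 days. A rule that looks only at distance from Day 80 ignores that separation. If an unscheduled visit happens to lie nearer Day 80, its value becomes the Visit 5 value although the subject is on drug or barely off it. This matters most for the engraftment measures: a swab or strip taken within a day or two of application may pick up applied product rather than organisms that have persisted. Follicular success also defines a subgroup in SAP 8.11.4.5.

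For Screening, the stake is different. That value is the reference for every change endpoint and the MMRM covariate, so it needs one definition that a programmer can apply without judgement.

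**Working it through.** **1. Reproduce the plan's own figures.**
- SAP 8.8 expects the final dose on Days 73-77. From Visit 5 on Day 80 and a gap of 3-7 days: 80 − 7 = 73 and 80 − 3 = 77, which agrees. The midpoint, 75, is the SAP's dose denominator.
- The mITT boundary between Visits 4 and 5 is (43 + 80)/2 = 61.5, which agrees with >61.
- The PP windows for Visits 3 and 4 agree with the schedule: 8 ± 2 = 6-10 and 43 ± 7 = 36-50.
- The Visit 5 PP window, 71-90, does not follow from +3 to +7 days.

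**2. Displacement condition.** Let L be the last-dose day, V the scheduled Visit 5 day and U the unscheduled day, with U before V and inside the window. U replaces V if |U − 80| < |V − 80|. U is too early off drug if U − L ≤ 2.

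**3. Adherent timing.** L = 73 to 77 and V = L + 3 to L + 7 give 5 × 5 = 25 combinations. Displacement by a value less than 3 days off drug is possible in four:

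| L | V | \|V − 80\| | Displacing U (distance; days since last dose) |
|---|---|---|---|
| 76 | 83 | 3 | 78 (2; 2) |
| 77 | 82 | 2 | 79 (1; 2) |
| 77 | 83 | 3 | 78 (2; 1), 79 (1; 2) |
| 77 | 84 | 4 | 77 (3; 0), 78 (2; 1), 79 (1; 2) |

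For L of 75 or less, V is at most 82 and U at most 77, so no such U is nearer to Day 80. If U must be on or before the last-dose day, only L = 77, V = 84, U = 77 remains: 1 of 25. A Visit 5 on Day 80 cannot be displaced.

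Ties also arise with no rule to settle them. For L = 77 and V = 81, U = 79 is equally distant (1 day). For L = 76 and V = 82, U = 78 is equally distant (2 days).

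**4. Later Visit 5, counting only U on or before the last-dose day.**
- L = 77, V = 87: U = 74-77 displaces it, within PP limits.
- L = 77, V = 95: U = 66-77 displaces it, in mITT.
- If the schedule's +3 to +7 is read as Days 83-87, with a 3-7 day gap: 23 of 25 combinations.
- Under the PP limits of SAP 8.2.3 (V on Days 71-90, gap 1-10 days): 75 of 200 combinations.

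These are counts of possible calendars, not probabilities.

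**5. Follicular strips.** Here the route is SAP 8.9.2 rather than the nearest-day rule. If a visit means everything inside its Table 3 window, an on-drug strip from an unscheduled visit after Day 61 belongs to Visit 5 in mITT. It then enters the mean, and one positive strip makes the subject a success. The SAP does not say whether the nearest-day rule is applied before or instead of 8.9.2.

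**6. Screening.** With the target equal to the window, the distance is 0 for every day from −28 to −1; Days −14, −5 and −1 all tie. The rule selects nothing. The window also reaches 14 days further back than the protocol's Day −14 to −1, which the SAP's own Table 1 repeats.

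**7. After the change.** With the scheduled record taking precedence, 0 of the 25 combinations allow displacement.

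**The case against.** The strongest reply is that the exposure is small and partly covered. On the SAP's own timing, only 1 of 25 combinations admits a truly on-drug substitute, and the wider counts need a late Visit 5 or a reading of +3 to +7 that footnote p does not favour, since it counts from the final application. The follicular endpoint is already tied to EOT in SAP 3.2 and 8.9.2, SAP 6.4 lists follicular sampling only at Screening and Visit 5, and the multiple samples in 8.9.2 are probably replicate strips. The endpoints are exploratory, the study is not powered, and by-subject listings would show a substitution.

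Most of this stands and limits the size of the point. It does not remove it. The PP condition on Visit 5 timing decides who is in the population, not which record is used. SAP 6.4 conflicts with Protocol 6.2.5 and with the SAP's own Table 1, which both include strips at unscheduled visits. A listing exposes a substituted value but does not settle which one the analysis should use.

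Four stronger readings are tempting and not supported:
- **That the rule favours a Screening value taken during BPO.** It favours none, because all days tie. The scheduled Screening value is pre-BPO by footnotes i and n. A competing value would need an extra assessment between the start of BPO and Day 1, and the unscheduled column sits under the Treatment period.
- **That substituted values are selected by flares or differ by arm.** Protocol 6.2.5 names no trigger for an unscheduled visit, and nothing in the documents indicates an imbalance.
- **That a particular number of subjects is affected.** The documents give no rate of unscheduled visits.
- **That Visit 4 is harmed in the same way.** There one on-treatment value gives way to another nearer Day 43, which is what the rule is for.

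**Conclusion.** The point holds in a limited form. Followed literally, SAP 8.1 lets an unscheduled value 0-2 days after the last dose replace the scheduled Visit 5 value in mITT and in PP, and SAP 8.9.2 does not keep an unscheduled on-drug strip out of the follicular result. The opportunity is narrow when dates are kept (4 of 25 combinations) and widens as Visit 5 slips. The count assumes last doses on Days 73-77, gaps of 3-7 days and an unscheduled visit that yields the endpoint; how often that happens is unknown.

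For scale only: with 36 subjects split 2:1, the nominal NB01 arm is 24, so one changed follicular result would move its proportion by 1/24 = 4.2 percentage points. Nothing shows that any result would change.

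The Screening rule is undefined rather than biased, and its window disagrees with the protocol. The primary safety analyses of adverse events and the conduct of the trial are untouched. This is a clarification worth making, not a threat to the study's main conclusion.

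**What to change.** - **SAP 8.1:** use the scheduled visit's record whenever one falls in the window; use an unscheduled record only if the scheduled one is missing; state a rule for ties among the remaining records. Say whether EOT procedures done at early discontinuation count as scheduled.
- **SAP 5 and 8.9.2:** restrict follicular success and the marker means to strips taken at the scheduled Visit 5/EOT, and say that the multiple samples are replicates from that visit, if that is what is meant.
- **Screening:** define the analysis value as the last one before the first BPO application, in place of the range now given as the target day. Reconcile the −28 to −1 window with the protocol's Day −14 to −1.
- **Visit 5 timing:** reconcile Day 80, +3 to +7 days and the PP window of Days 71-90.
- List unscheduled values separately.

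The cost is a few sentences and one programming flag, with no new data. The text should be settled before the data freeze and unblinding of the project statistician described in SAP 8.3, so that records are not chosen with treatment known.

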8.2 Analysis Populations

8.2.1 *Safety Population*

The Safety population will include all randomized subjects who received and applied study drug. Subjects will have their first application of test article applied in the clinic by the PI (or sub-I-designee) during their Baseline Visit on Day 1. Subjects will be included in a treatment group based on the treatment they received (even if not the treatment group to which they were randomized). If a subject administered more than one type of test article during the trial, then the subject will be included in the treatment group to which they were randomized.

8.2.2 *Modified Intent-to-Treat Population*

The modified intent-to-treat (mITT) population will include all randomized subjects who were dispensed the study drug and have at least one post-baseline assessment. Subjects will be included in the treatment group to which they were randomized, regardless of the treatment received.

8.2.3 *Per-Protocol Population*

The per-protocol (PP) population will include a subset of the mITT population who completed the study without significant protocol deviations (as will be determined prior to unblinding the randomization) and met the criteria as specified below. Subjects will be included in the treatment group based on the treatment received.

- Meets all inclusion criteria and does not meet exclusion criteria #1-11 and #13-22.
- Has not taken or applied any interfering concomitant medications/therapies.
- Completed Visit 5/EOT procedures on Days 71 to 90 with the visit occurring 1 to 10 days after the final application of test article.
- Applied at least 80% of the expected doses with no other evidence of material dosing non-compliance.

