6.1.2. Subject Replacement

If a subject is discontinued from the study for any reason other than a dose-limiting toxicity (DLT; see [Section 7.2.1](#)) prior to the completion of Week 2/Visit 3, that subject will be replaced.

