8.2.2. Intent-to-Treat Population

The ITT population will include all randomized subjects who were dispensed the study drug.

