8.4.4. Exploratory Efficacy Analyses

The efficacy analyses will be conducted on the ITT and PP populations.

Investigator’s Global Assessment

The observed and change from Screening scores at each follow-up visit will be tabulated. For endpoint of IGA, the treatment groups will be compared with respect to the proportions of subjects with (a) at least a one-point improvement and (b) at least a two-point improvement in IGA score relative to Screening at each follow-up visit using the CMH test with and without stratification on study center.

Acne Lesion Counts

For endpoint of Acne Lesion Counts, the absolute and percent change from Screening at each follow-up visit in total, inflammatory, and non-inflammatory lesions, the comparison between NB01 and vehicle-control will be analyzed using Analysis of Covariance (ANCOVA) model with the factor treatment and the Screening counts as a covariate in the model, with and without Last Observation Carried Forward (LOCF) imputation.

Acne Quality of Life

For endpoint of Acne-QoL, the absolute and percent change from Screening at each follow-up visit on four domains separately and total, the comparison between NB01 and vehicle-control will be analyzed using ANCOVA model with the factor treatment and the Screening score as a covariate in the model, with and without LOCF imputation.

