8.11 Exploratory Efficacy Evaluation

The efficacy analyses will be conducted on the mITT and PP populations.

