8.11.4 Statistical / Analytical Issues

8.11.4.1 Handling of Dropouts or Missing Data

The primary method of handling missing data will be the MMRM method without explicit imputations for missing data. Since IGA is analyzed based on a “success” criteria (one- or two-point improvement in score), subjects with a missing IGA score will be considered a “failure” in the analysis for the mITT population. Analyses in the PP population will use observed data only.

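### The SAP's mITT set can drop dosed subjects lost before any later assessment, so its missing-IGA-equals-failure rule cannot reach them; SAP Section 9 does not list the change from ITT

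*SAP*

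**What the plan says.** Protocol 8.2.2 sets no condition on follow-up: "The ITT population will include all randomized subjects who were dispensed the study drug". Protocol 8.4.4 then states: "The efficacy analyses will be conducted on the ITT and PP populations".

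SAP 8.2.2 defines a modified set instead. Subjects must be randomised, be dispensed drug and "have at least one post-baseline assessment". SAP 8.11 follows this through: "The efficacy analyses will be conducted on the mITT and PP populations". No analysis on the protocol's ITT set remains.

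For the one-point and two-point IGA responder endpoints, SAP 8.11.4.1 says that "subjects with a missing IGA score will be considered a “failure” in the analysis for the mITT population". The same section has the PP analyses use observed data only, and SAP 8.2.3 makes PP a subset of mITT.

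SAP Section 9 records four changes from the protocol: the reference visit, EOS to EOT for engraftment, absolute to observed change, and ANCOVA with LOCF to MMRM. The move from ITT to mITT is not among them.

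**The concern.** Counting a missing IGA as failure is meant to stop dropouts from improving a responder rate. It works only for subjects who are in the analysis set. SAP 8.2.1 has the first dose applied in clinic on Day 1, and the schedule of events has drug dispensed at the same visit. A subject who leaves afterwards and is never assessed again has therefore been randomised, dosed and dispensed drug. The protocol would keep that subject in the efficacy denominator. The SAP removes the subject before the missing-data rule applies.

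Leaving that early may be related to treatment. Protocol 1.4 names irritation, dryness, redness and worsening of disease as possible risks. In a trial of 36 subjects, one or two exclusions are enough to shift a responder rate and its p-value noticeably. Because Section 9 is silent, a reader of the study report would not be told that the efficacy population differs from the one in the protocol.

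**Working it through.** The documents give no dropout rate, responder rate, power or alpha, so there is no figure in the plan to reproduce. What can be checked is the effect of the definition.

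**Inputs**
- Randomised: 36 (Protocol 3.3), allocated 2:1 (Protocol 5.1.1; SAP 8.5). Nominal arms: 36 × 2/3 = 24 NB01 and 36 × 1/3 = 12 vehicle. Stratification or replacement could make the actual arms differ slightly.
- Test: CMH without stratification, one of the two versions in SAP 8.11.1.
- Assumed, not in the documents: the number k excluded in an arm, and the responder counts.

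**Rate within an arm.** Let r be the responders among n subjects, and let k be the subjects with no post-baseline assessment. None of the k can be an observed responder. The ITT rate with missing as failure is r/n and the mITT rate is r/(n − k), so the inflation factor is n/(n − k).

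| k | NB01, 24/(24 − k) | Vehicle, 12/(12 − k) |
|---|---|---|
| 0 | 1.000 | 1.000 |
| 1 | 24/23 = 1.043 | 12/11 = 1.091 |
| 2 | 24/22 = 1.091 | 12/10 = 1.200 |
| 3 | 24/21 = 1.143 | 12/9 = 1.333 |

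Within an arm the shift is upward or zero, never downward.

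**Treatment comparison.** Let a be the NB01 responders, m all responders, n1 and n2 the arm sizes, and N = n1 + n2. Then E = n1·m/N, V = n1·n2·m·(N − m)/(N²(N − 1)), and the statistic (a − E)²/V has 1 degree of freedom. Assume 12 NB01 responders and 2 vehicle responders, so m = 14.

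- Full set, 12/24 v 2/12: E = 9.333, V = 1.956, statistic 3.64, p = 0.057.
- One NB01 exclusion, 12/23 v 2/12: E = 9.2, V = 1.948, statistic 4.02, p = 0.045.
- One vehicle exclusion, 12/24 v 2/11: E = 9.6, V = 1.864, statistic 3.09, p = 0.079.

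| Excluded (NB01, vehicle) | Rates | Difference, points | p |
|---|---|---|---|
| 0, 0 | 50.0% v 16.7% | 33.3 | 0.057 |
| 1, 0 | 52.2% v 16.7% | 35.5 | 0.045 |
| 2, 0 | 54.5% v 16.7% | 37.9 | 0.035 |
| 0, 1 | 50.0% v 18.2% | 31.8 | 0.079 |
| 0, 2 | 50.0% v 20.0% | 30.0 | 0.111 |
| 1, 1 | 52.2% v 18.2% | 34.0 | 0.063 |

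The direction depends on which arm loses the subjects. With 12/24 v 3/12 instead (p = 0.157), one NB01 exclusion gives p = 0.129 and one vehicle exclusion gives p = 0.214. The pattern is the same, but 0.05 is not crossed.

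**The case against.** The strongest reply is that few subjects, perhaps none, will be affected.

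- **Any assessment qualifies.** SAP 8.2.2 does not ask for an IGA. A reader might infer that every subject without a post-baseline IGA is dropped, but the text does not say so. A subject with a later skin-reaction or adverse-event assessment and no IGA is in mITT and counts as a failure. Whether a diary entry, a telephone contact or the 30-minute check after the Day 1 dose would qualify is left open. This narrows the problem, but leaves membership of the set open to interpretation.
- **Early leavers are called back.** Protocol 3.6, 6.3 and 10.2 call for EOT procedures at early discontinuation, and Protocol 7.2.1 schedules a final visit after a DLT. Anyone who attends is in mITT. Protocol 3.6 also provides for subjects who will not return, and they are the ones at issue.
- **Exclusions will be visible.** SAP 8.6 tabulates the number in each population, and withdrawals with reasons, by arm. A careful reader could rebuild the ITT rate. That helps, but does not replace the planned analysis.
- **The endpoints are exploratory.** No alpha is stated, no multiplicity adjustment is planned, and the primary safety analysis uses all subjects who applied drug. Crossing 0.05 settles no planned decision. This limits the weight of the point.

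A reader might also see a second loss in Protocol 6.1.2, under which a subject discontinued for a reason other than a DLT "prior to the completion of Week 2/Visit 3, that subject will be replaced". That clause governs enrolment. Nothing in it removes the replaced subject from an analysis set.

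**Conclusion.** The point holds in a conditional form. The SAP narrows the protocol's efficacy population without recording the change, and the narrowed set lets some dosed subjects escape the SAP's own missing-equals-failure rule. If k subjects in an arm of n are lost with no later assessment, the IGA responder rate in that arm is inflated by n/(n − k). One loss means 4.3% (NB01) or 9.1% (vehicle) in relative terms at nominal arms of 24 and 12.

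Two stronger readings are tempting. One is that the reported responder rates are overstated. The documents give no dropout count, and with k = 0 nothing changes. The other is that the comparison is tilted towards NB01. Losses on vehicle shrink the difference, and the p-values above rest on assumed counts.

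The scope is the two IGA responder endpoints. The MMRM analyses gain nothing from subjects with no post-dose value, the missing-equals-failure rule does not name follicular success, and the primary safety analysis is untouched. The undisclosed change of population stands whatever the dropout count. The change below is worth making because it restores the protocol's own set at almost no cost.

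**What to change.** 1. Run the one-point and two-point IGA responder analyses on the protocol ITT set: all randomised subjects dispensed study drug, including any later replaced, with a missing IGA counted as failure.
2. Keep mITT for the MMRM analyses and, while editing SAP 8.2.2, state which assessment qualifies a subject.
3. List the change from ITT to mITT, and where each set is used, in SAP Section 9.

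Do not extend missing-equals-failure to follicular engraftment success as part of this change. The SAP rule covers IGA only, and the extension would score an unsampled subject as having no live NB01.

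The cost is SAP wording, with no new data and no change to conduct. It should be settled before the initial data freeze in SAP 8.3, when the populations are identified and the project statistician is unblinded. The downside is that responder rates may be slightly less favourable.
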